## CHAPTER THREE

### RESULTS

There were total 15 subjects who completed the 6-month trial. There were 10 males with an mean age of 55.6 years and 8 males with an mean age of 51.1 years. There was a total of 3 patients in SRP group, 3 patients in HP13 group, and 9 patients in HP26 group. The mean pocket depth (PD) shown in figure 1 at baseline for SRP group was  $3.88 \pm 0.06$  mm (std. error),  $4.11 \pm 0.06$  mm for HP13, and  $3.83 \pm 0.04$  mm for HP26. At the 4-week examination, PD for SRP group decreased to  $3.67 \pm 0.06$  mm,  $4.06 \pm 0.06$  mm with HP13, and  $3.55 \pm 0.04$  mm for HP26. At the re-evaluation examination, PD for SRP group was  $3.30 \pm 0.06$  mm,  $3.43 \pm 0.06$  mm for HP13, and  $3.14 \pm 0.04$  mm for HP26. The final examination, PD were  $3.43 \pm 0.06$  for SRP,  $3.40 \pm 0.06$  mm for HP 13, and  $3.23 \pm 0.04$  mm for HP26. Repeated measure ANOVA showed significant difference in pocket depth among all time points in all treatment groups. In SRP group, no significant difference between baseline and 4 weeks in pocket depth and relative attachment level.

[figure not shown]

Figure 2. Mean PD in each group, SRP, HP13, and HP26.

Figure 2 shows the mean relative recession over time. The mean relative recession at baseline was  $3.28 \pm 0.06$  mm for SRP,  $2.87 \pm 0.06$  mm for HP13, and  $3.21 \pm 0.03$  mm for HP13. At 4-weeks, it was  $3.35 \pm 0.06$  mm for SRP,  $3.23 \pm 0.05$  mm for HP13, and  $3.15 \pm 0.03$  mm for HP26. At re-evaluation it was  $3.33 \pm 0.06$  mm for SRP,  $3.27 \pm 0.05$  mm for HP13, and  $3.29 \pm 0.03$  mm for HP26.

[figure not shown]

Figure 3. Mean R-Rec in each group, SRP, HP13, and HP26.

Figure 3 shows the mean relative attachment level. The mean RAL at baseline was  $7.16 \pm 0.08$  mm for SRP,  $6.97 \pm 0.07$  mm for HP13, and  $7.04 \pm 0.04$  mm for HP26. At 4-weeks, the RAL was  $7.02 \pm 0.08$  mm for SRP,  $7.29 \pm 0.07$  mm for HP13, and  $6.69 \pm 0.05$  mm for HP26. At re-evaluation the RAL was  $6.63 \pm 0.08$  mm for SRP,  $6.15 \pm 0.07$  mm for HP13, and  $6.39 \pm 0.04$  mm for HP26. At the final exam RAL was  $6.79 \pm 0.08$  mm for SRP,  $6.71 \pm 0.07$  mm for HP13, and  $6.53 \pm 0.04$  mm for HP26.

[figure not shown]

Figure 4. Mean RAL in each group, SRP, HP13, and HP26.

Figures 4, 5, 6, and 7 show baseline, 4-week, re-evaluation, and final MQH plaque scores. Plaque scores varied throughout the four timepoints with no obvious differences between groups.

[figure not shown]

Figure 5. Baseline MQH scores for A) SRP, B) HP13, and C) HP26

[figure not shown]

Figure 6. 4-Week MQH scores for A) SRP, B) HP13, and C) HP26.

[figure not shown]

Figure 7. Re-Evaluation MQH scores for A) SRP, B) HP13, and C) HP26.

[figure not shown]

Figure 8. Final MQH scores for A) SRP, B) HP13, and C) HP26.

[figure not shown]

Figure 9. Mean BOP in each group, SRP, HP13, and HP26

[figure not shown]

Figure 10. BOP % in pockets initially <5 mm

[figure not shown]

Figure 11. BOP % in pockets initially  $\geq 5$ mm

Figure 8 shows mean BOP. Baseline mean BOP was 45% for SRP, 57% for HP13, and 63.1% for HP26. At 4-weeks, mean BOP was 45% for SRP, 60% for HP13, and 44% for HP26. At re-evaluation, mean BOP was 37% for SRP, 30% for HP13, and 27% for HP26. Final mean BOP scores were 44% for SRP, 33% for HP13, and 28% for HP13. Mean BOP was significantly reduced in all groups between 4-week examination and re-evaluation with mean BOP scores at final examination staying similar to levels at re-evaluation for HP13 and HP26 groups. Mean BOP scores at final examination group for SRP group was similar to baseline.

Figure 9 shows BOP % in pockets initially  $< 5$ mm. At baseline, 24% of pockets  $< 5$ mm were BOP for SRP, 47% for HP13, and 52% for HP26. At 4-week examination BOP % were 29% for SRP, 44% for HP13, and 35% for HP26. At re-evaluation, BOP %

was 27% for SRP, 21% for HP13, and 22% for HP26. At the final exam, BOP % was 33% for SRP, 26% for HP13, and 22% for HP26.

Figure 10 shows BOP % in pockets initially  $\geq 5$ mm. At baseline, BOP % was 92% for SRP, 81% for HP13, and 91% for HP26. At 4-week examination, BOP % was 91% for SRP, 93% for HP13, and 83% for HP26. Re-evaluation BOP % was 91% for SRP, 78% for HP13, and 75% for HP26. At final examination, BOP % was 88% for SRP, 79% for HP13, and 78% for HP26.

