## ABSTRACT OF THE THESIS

Custom Application of Peroxide Gel as Adjunct to Scaling/Root planning in Treatment of Periodontitis

by

[name]

Master of Science, Graduate Program in Periodontics

Loma Linda University, September 2019

[name] [name], Chairperson

**Aim:** This study was aimed to evaluate and compare the clinical effects of scaling and root planning (SRP) combined with local delivery of 1.7% HP in customized trays to that of SRP alone.

**Materials and Methods:** Sixty patients with generalized moderate to chronic severe periodontitis will be assigned to three groups treated by SRP plus HP gel with a custom prescription tray application. The test groups will receive twice daily 1.7% HP gel in custom trays four weeks prior to SRP and will continue to application for up to 3- and 6-months post-SRP. Baseline data that is collected at the start of the study will be collected again at 4, 13, and 26 weeks post-SRP and analyzed for any changes and thus main outcome variables will include changes in pocket depth (PD), relative recession (R-Rec), relative attachment level (RAL), and changes in bleeding (BOP) using ANCOVA of main effects.

**Results:** Repeated measure ANOVA showed significant difference in pocket depth among all time points in all treatment groups. Mean BOP was significantly reduced in all groups between 4-week examination and re-evaluation with mean BOP scores at final

examination staying similar to levels at re-evaluation for HP13 and HP26 groups. Mean BOP scores at final examination group for SRP group was similar to baseline.

**Discussion:** The use of adjunctive HP in custom fabricated trays presents with no adverse effects. Significant improvement was evident in pocket depth and attachment level in both treatment groups between after 4 weeks of using the tray. No significant effect found in SRP group between baseline and 4 weeks. After SRP, significant difference was seen in all three groups between 4 weeks and 3 months.

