#### **Screening and Recruitment of Participants**

A study population of sixty qualifying adults was selected by screening from patients who were referred to the Graduate Periodontics Clinic at Loma Linda University School of Dentistry. All patients received a comprehensive periodontal examination and those diagnosed generalized moderate to severe chronic periodontitis  showing minimum of one site with PD of  $\geq 5$  mm and bleeding on probing (BOP) in at least two quadrants was considered for subject recruitment. Patients who met the inclusion and exclusion criteria were eligible to participate in the study (see Eligibility and Exclusion criteria) and the patients were asked if they were willing to be a subject. Verbal and written informed consent were given to the subject outlining the purpose, timeline, as well as potential risks and benefits of participation. Once the patient accepted and was recruited as a subject they were randomized into groups by a predetermined random group assigner (see Randomization: Sequence, Allocation, and Implementation).

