## **Exclusion Criteria**

- 1) Any systemic conditions or medication intake that can alter periodontal status (e.g. uncontrolled diabetes (with <3-month recent HbA1c of  $>8.5\%$ ), anti-seizure medication, immunosuppressant, and calcium channel blockers with clinical sign of gingival overgrowth.
- 2) Immune-compromised state.

- 3) Any current heavy smoking habits (>10 cigarettes/day)
- 4) Any medical condition or history requiring prophylactic antibiotic coverage prior to dental treatment.
- 5) Females who are lactating or pregnant (as determined by medical history) or planning to become pregnant for the duration of the study.
- 7) Physical limitations/restrictions compromising oral hygiene procedures.
- 8) The presence of significant oral soft tissue pathology and/or lesions associated with ill-fitting appliances or restorations.
- 9) Tooth mobility associated with advanced periodontal disease (e.g. score of >2 using Miller Classification).
- 10) Any temporomandibular joint disorders.
- 11) Grossly carious, orthodontically banded, and third molars will not be included in the tooth count.
- 12) Presence of any significantly tipped, crowded, or largely defective restorations.
- 13) Any extreme adverse events relating to the use of HP gel (e.g. prolonged tooth hypersensitivity or aberrant soft tissue/mucosal reaction)

All participants were screened and evaluated at Loma Linda University School of Dentistry Graduate Periodontics Department. There are three groups of 20 patients, two therapy test groups and the control group.

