## **Statistical Analysis**

The primary outcome variables are PD reduction, RAL gain, and reduction in BOP. PD data was computed to provide a mean score per mouth. Secondary efficacy variables were BOP, and MQH. BOP was computed to provide a mean score per mouth for each clinical assessment and were analyzed using repeated measures (ANOVA). Outcome variable data analysis consisted of between-treatment and within-treatment (longitudinal) comparisons of PD and CAL at all examination time points using parametric procedures. Between-treatment and within-treatment comparisons employed baseline data and analysis of covariance (ANCOVA) for follow-up data. All comparisons were performed using two-sided hypothesis tests, and employed a 0.05 level of significance.

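### The analysed population is inconsistent (15 completers by arm, 18 people in the demographics), and the results appear to be a completer analysis although no rule says so

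*Combined protocol and SAP*

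**What the plan says.** Planned size: the Abstract says "Sixty patients with generalized moderate to chronic severe periodontitis will be assigned to three groups", the recruitment section says "A study population of sixty qualifying adults was selected by screening", and the text closing the exclusion criteria says "There are three groups of 20 patients, two therapy test groups and the control group".

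Reported size: Chapter Three opens with "There were total 15 subjects who completed the 6-month trial". The next sentence reads "There were 10 males with an mean age of 55.6 years and 8 males with an mean age of 51.1 years", and the one after that "There was a total of 3 patients in SRP group, 3 patients in HP13 group, and 9 patients in HP26 group".

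Method: under Statistical Analysis, per-mouth BOP scores "were analyzed using repeated measures (ANOVA"). The same section names ANCOVA with baseline data for the between- and within-treatment comparisons. Chapter Three then reports a repeated-measures ANOVA for PD. Tests are two-sided at 0.05.

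The text defines no analysis population, no rule for patients with missing visits, and no count of patients measured at each visit. The only stated exclusion of collected data is at site level, for re-treated sites (Follow Up Care).

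**The concern.** Three adjacent sentences cannot all describe one set of people. A reader cannot tell whether a given mean rests on 15 patients, on 18, or on a number that changes by visit.

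Two things could be at stake. First, completing week 26 happens after randomisation and may depend on the burden of the trays or on response. A set chosen by completion is then no longer protected by randomisation. Second, the second primary objective in the Introduction asks whether the gel lowers inflammation before SRP. Week 4 answers that question, and attendance at week 26 has no bearing on it. A method that needs all four visits would drop a patient from the week-4 comparison for a reason unrelated to it.

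Week 4 is also where the small arms look least stable. HP13 and HP26 follow the same regimen up to week 13. Yet between baseline and week 4, BOP moved from 57% to 60% in HP13 and from 63.1% to 44% in HP26. RAL moved from 6.97 to 7.29 mm and from 7.04 to 6.69 mm.

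**Working it through.** **Counts.** Arms: 3 + 3 + 9 = 15, which reproduces the stated completers. Plan: 3 × 20 = 60, which reproduces the planned total. Demographics: 10 + 8 = 18, which does not reproduce 15. The excess is 18 − 15 = 3 people, or 3/18 = 17% if 18 were enrolled.

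**Is it one fixed set of 15?** Two indirect checks on the reported standard errors (SE):

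- The PD SEs are 0.06, 0.06 and 0.04 mm (SRP, HP13, HP26) at all four visits. A fixed set would give this. A model that pools variance over visits could too.
- If site-level SDs and tooth counts are similar, the size ratio HP26:SRP is about (SE of SRP / SE of HP26)². Allowing ±0.005 for rounding, with the baseline SEs:
  - PD: from (0.055/0.045)² = 1.49 to (0.065/0.035)² = 3.45
  - R-Rec: from (0.055/0.035)² = 2.47 to (0.065/0.025)² = 6.76
  - RAL: from (0.075/0.045)² = 2.78 to (0.085/0.035)² = 5.90
  - The common range is 2.78 to 3.45, which contains 9/3 = 3.

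Both checks support a fixed set of 15. Neither proves it.

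**Sensitivity of PD to three further patients, if they exist.** Their arms are not stated, so two extremes are shown.

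Week 26: mean changes are 3.43 − 3.88 = −0.45 mm (SRP) and 3.23 − 3.83 = −0.60 mm (HP26), a difference of −0.15 mm. It vanishes in either of these cases:

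- All three were SRP and averaged x, where (3 × −0.45 + 3x)/6 = −0.60, so x = −0.75 mm.
- All three were HP26 and averaged x, where (9 × −0.60 + 3x)/12 = −0.45, so x = 0.00 mm.

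Non-completers would have no week-26 value, so this shows sensitivity to unseen outcomes.

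Week 4, where such patients could have been measured: changes are 3.67 − 3.88 = −0.21 mm (SRP) and 3.55 − 3.83 = −0.28 mm (HP26), a difference of −0.07 mm. It vanishes if three more SRP patients averaged −0.35 mm, since (3 × −0.21 + 3 × −0.35)/6 = −0.28. It also vanishes if three more HP26 patients averaged 0.00 mm, since (9 × −0.28 + 0)/12 = −0.21.

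**Precision regained.** Detectable SRP–HP26 difference at 80% power, two-sided 0.05, normal approximation: (1.960 + 0.842) × √(1/n₁ + 1/n₂) in SD units. Values from the t distribution are alongside.

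| SRP vs HP26 | Normal | t |
|---|---|---|
| 3 vs 9 (as reported) | 1.87 | 2.07 |
| 6 vs 9 (all three SRP) | 1.48 | 1.60 |
| 3 vs 12 (all three HP26) | 1.81 | 1.96 |
| 20 vs 20 (planned) | 0.89 | 0.91 |

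If all three were HP13, this comparison is unchanged. Even complete data on 18 would stay far from the planned precision.

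**The case against.** The strongest reply is that a completers-only rule is inferred. The document says who completed and gives arm sizes; it does not define who was analysed. That stands.

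The 18 may also be a slip. The sentence already labels both groups males, and nearby text has similar errors: HP13 is named twice in the baseline recession values and again in the final BOP values. Nothing shows that three extra people, if real, had a week-4 or week-13 measurement. A reader might infer that collected data were discarded; the document does not show that.

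The mechanism is not certain either. ANCOVA is named alongside repeated-measures ANOVA, and a week-4 ANCOVA would need only baseline and week 4. But repeated-measures ANOVA is the method stated for BOP and reported for PD, and the handling of incomplete patients is described for neither method.

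A reader might also take 60 planned and 15 completed as heavy dropout, and 3, 3 and 9 as unequal retention. The text does not support this. Completion would be 15/60 = 25% if 60 were randomised and 15/18 = 83% if 18 were. Under-recruitment fits as well as loss. Numbers by arm may be in the CONSORT diagram, which is not reproduced in the text reviewed, so their absence is no fault of the plan.

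Finally, a mixed model on so few patients is fragile and still assumes that data are missing at random. That is a fair limit on the remedy, and the precision table agrees.

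**Conclusion.** The concern holds in a limited form. The contradiction between 15 and 18 is certain and unreconciled, as is the lack of a stated analysis population and missing-data rule. That the results are a completer analysis is the most likely reading: the only arm sizes are completer counts, the SEs fit a fixed 3:9 split, and the method drops incomplete cases in its classical form. It remains an inference.

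The possible omission is at most three patients, 17% of 18, and only if the 18 is real and they attended a follow-up visit. With three patients in two arms that number is enough to matter: under the extremes shown, plausible values would remove the PD difference between SRP and HP26. The case rests on comparability and on knowing who is in each mean. It does not rest on power. No dropout rate and no difference in retention between arms can be claimed from the text.

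**What to change.** 1. Reconcile 15 with 18 and correct the sex labels, so that the demographics describe the analysed set.
2. Define the analysis population, and tabulate by arm the number with data at baseline and weeks 4, 13 and 26. The week-4 column needs care: the SRP visit schedule lists no week-4 measurement, yet Chapter Three reports a week-4 mean for that arm.
3. Replace the repeated-measures ANOVA with a likelihood-based mixed model for repeated measures on patient-mean outcomes. Use arm, visit, arm-by-visit and baseline as fixed effects and patient as a random effect. Include every randomised patient with any post-baseline visit, in the assigned arm.
4. Show the completer result as a sensitivity analysis.

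The cost is one table and one standard model. If 18 proves to be a typing error and all 15 have every visit, step 1 settles the denominator and the model loses no one. The drawbacks are that the model assumes data are missing at random, that its estimates will be fragile with three patients in two arms, and that the precision gain is modest at best. The report should say so.

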method combining mechanical and chemical debridement with 1.7% HP gel . The HP gel is directed into periodontal pockets via a custom tray, as an aid to manage biofilms better for patients with gingivitis and periodontitis. The FDA approved  $\leq 3\%$  HP gel as an oral debriding agent and an oral wound cleanser. The FDA also cleared the prescription tray branded as the Perio Tray® (Perio Protect, St. Louis, MO) as a subgingival delivery medical device in 2004 (21 C.F.R. § 872.6870). Customized extensions of the tray support the customized seal to direct the gel deep down into the sulcus or periodontal pocket and overcome the crevicular fluid flow .

Custom tray application of the HP gel as an adjunct to SRP in the treatment of chronic periodontitis has been investigated. In randomized controlled studies, it was demonstrated that significant reduction of probing depth (PD) and bleeding without mechanical intervention were seen after two weeks of HP prescription tray regimen followed by SRP and the results were maintained for up to six months with the daily use of HP prescription trays for 10 weeks . The prescription tray delivery of HP gel as an adjunctive to SRP was effective before and after full-mouth SRP in reducing PD about 1mm over SRP alone for six months in chronic periodontitis patients . However, there is currently no randomized control clinical study evaluating the differences in the duration effects of the treatment in chronic periodontitis patients with customized delivery of hydrogen peroxide gel.

The primary objectives of this randomized, controlled, single-blind, parallel clinical study are: (1) to examine if the prescription tray delivery of HP gel adjunctive to SRP results in a greater clinical improvement than SRP alone over a six-month period; and (2) to

evaluate whether the custom tray delivery of the HP gel can decrease inflammation prior to SRP.

The secondary objective is to compare if there is a difference between the length of treatment of adjunctive HP gel (3-months versus 6-months). It is hypothesized that adjunctive HP therapy will provide additional clinical benefits in PD reduction, attachment gain, and reduction of bleeding on probing (BOP) compared to SRP alone.

Null Hypotheses:

There is no significant difference between the treatment groups (SRP + HP13 vs. SRP + HP26 vs. SRP alone) with regards to reduction in PD.

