There is no significant difference between the treatment groups with regards to attachment gain.

There is no significant difference between the treatment groups with regards to BOP.

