## **CHAPTER FIVE**

### **CONCLUSION**

In conclusion, the use of adjunctive HP in custom fabricated trays presents with no adverse effects. Significant improvement was evident in pocket depth and attachment level in both treatment groups between after 4 weeks of using the tray. No significant effect found in SRP group between baseline and 4 weeks. After SRP, significant difference was seen in all three groups between 4 weeks and 3 months.

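### No six-month between-arm result for pocket depth or attachment is reported; a time-effect ANOVA and within-arm statements stand in its place and cannot show a gel effect

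*Combined protocol and SAP*

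**What the plan says.** **Question.** In Chapter One, primary objective 1 asks whether tray-delivered gel with SRP "results in a greater clinical improvement than SRP alone over a six-month period". The first null hypothesis is that the three arms do not differ "with regards to reduction in PD". The second reads "There is no significant difference between the treatment groups with regards to attachment gain". All of these are between-arm statements.

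**Plan.** Chapter Two, Statistical Analysis, states: "Outcome variable data analysis consisted of between-treatment and within-treatment (longitudinal) comparisons of PD and CAL at all examination time points using parametric procedures". It continues: "Between-treatment and within-treatment comparisons employed baseline data and analysis of covariance (ANCOVA) for follow-up data". PD is to be reduced to one mean per mouth, and testing is two-sided at 0.05. Repeated-measures ANOVA is named in connection with BOP. The Abstract also names ANCOVA.

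**Report.** For PD and RAL, Chapter Three gives arm means with standard errors, the sentence "Repeated measure ANOVA showed significant difference in pocket depth among all time points in all treatment groups", and a statement that SRP did not change significantly from baseline to week 4. The Abstract and Chapter Five repeat the SRP week-4 statement, claim significant week-4 improvement in PD and attachment in both gel arms, and add: "After SRP, significant difference was seen in all three groups between 4 weeks and 3 months". Neither null hypothesis 1 nor 2 is declared rejected or retained.

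**The concern.** All three arms received SRP. PD and RAL would be expected to change over the trial whether or not the gel works, so a significant time effect carries no information about gel. The statement that all three arms changed between week 4 and month 3 has the same limit. The week-4 statements cover a period before SRP, but finding significance in one arm and not in another is not a test of the difference between them.

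What is at stake is the main conclusion. As written, the Abstract and Conclusion stop at three months for PD and attachment. A reader is left with favourable within-arm statements and no answer, not even an inconclusive one, to the six-month question the trial was set up to ask.

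**Working it through.** The documents give no between-arm figure for PD or RAL, so there is none to reproduce. The inputs are the means printed in Chapter Three, in mm. RAL is measured from the stent margin to the pocket base, so a fall is a gain.

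| Outcome | Arm (completers) | Baseline | Week 4 | Week 13 | Week 26 | Improvement to week 26 |
|---|---|---|---|---|---|---|
| PD | SRP (3) | 3.88 | 3.67 | 3.30 | 3.43 | 0.45 |
| PD | HP13 (3) | 4.11 | 4.06 | 3.43 | 3.40 | 0.71 |
| PD | HP26 (9) | 3.83 | 3.55 | 3.14 | 3.23 | 0.60 |
| RAL | SRP (3) | 7.16 | 7.02 | 6.63 | 6.79 | 0.37 |
| RAL | HP13 (3) | 6.97 | 7.29 | 6.15 | 6.71 | 0.26 |
| RAL | HP26 (9) | 7.04 | 6.69 | 6.39 | 6.53 | 0.51 |

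**1. Six-month contrasts in change, gel minus SRP (positive favours gel).**
- PD: HP13 0.71 - 0.45 = +0.26; HP26 0.60 - 0.45 = +0.15.
- RAL: HP13 0.26 - 0.37 = -0.11; HP26 0.51 - 0.37 = +0.14.

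**2. Baseline-adjusted form.** An ANCOVA contrast is the week-26 difference corrected by a slope b times the baseline difference. No slope is given, so b is assumed to lie between 0 and 1 (b = 1 reproduces step 1).
- PD HP13: 0.03 + 0.23b, from +0.03 to +0.26.
- PD HP26: 0.20 - 0.05b, from +0.20 to +0.15.
- RAL HP13: 0.08 - 0.19b, from +0.08 to -0.11, changing sign at b = 0.08/0.19 = 0.42.
- RAL HP26: 0.26 - 0.12b, from +0.26 to +0.14.

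**3. Precision at patient level.** No SD of change is stated; 0.3 to 0.6 mm is assumed. The 95% half-width is t x SD x sqrt(1/n1 + 1/n2).
- 3 vs 9: 2.228 x SD x 0.667 = 0.45 to 0.89 mm.
- 3 vs 3: 2.776 x SD x 0.816 = 0.68 to 1.36 mm.

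Every contrast in steps 1 and 2 is smaller than the matching half-width.

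**4. Why the printed standard errors cannot settle it.** Their unit is not stated. If they are per patient, the implied PD SD in SRP is 0.06 x sqrt(3) = 0.10 mm. If they are per site, with an assumed 20 to 28 teeth and six sites each, it is 1.14 to 1.35 mm. The second looks more like a site-based error, contrary to the planned per-mouth mean. Taken at face value as patient-level, with an assumed baseline-to-final correlation of 0 to 0.8, t-based p-values for the step 1 contrasts run from 0.096 to 0.008 (PD HP13), 0.172 to 0.008 (PD HP26), 0.505 to 0.177 (RAL HP13) and 0.294 to 0.033 (RAL HP26). These depend too heavily on unstated quantities to be used.

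**5. Within-arm claims against the printed means, week 4.**
- PD fell 3.88 - 3.67 = 0.21 mm in SRP, reported as not significant. It fell 4.11 - 4.06 = 0.05 mm in HP13, covered by the claim of significant improvement in both gel arms. The standard error is 0.06 in each.
- HP13 RAL went from 6.97 to 7.29 mm, a worsening of 0.32 mm, under the same claim of improvement. The week-4 value agrees with its components (PD 4.06 + recession 3.23 = 7.29), so it does not look like an isolated misprint.
- Chapter Four says the study gave no evidence that gel before SRP reduced pocket depth, which is at odds with Chapter Five.

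Separately, HP13 RAL at week 13 is printed as 6.15 mm, although PD 3.43 + recession 3.27 = 6.70 mm. That value feeds the week-4 to month-3 statement but not the week-26 contrasts.

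**The case against.** The strongest reply is that the plan is sound and the analysis may have been done. Statistical Analysis says in the past tense that between-treatment comparisons were made at all time points, and Figures 2 and 4, which show PD and RAL by arm, are not in the readable text and might carry significance marks. This stands to the extent that a reader might infer that null hypotheses 1 and 2 were never tested, and the documents do not support that. What can be said is that no such result is reported in the readable Abstract, Results, Discussion or Conclusion. Marks on a figure would not fill that gap in the text.

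Four other inferences go too far:
- **That a time analysis of PD departs from the plan.** Within-treatment longitudinal comparisons of PD were planned by parametric methods. The gap is the missing companion contrast.
- **That the ANOVA sentence contradicts the SRP week-4 sentence, or HP13's 3.43 to 3.40 mm.** This holds only if it means every pair of time points. As an overall time effect it conflicts with neither.
- **That HP13 showed no attachment benefit, or harm.** HP13 improved on both outcomes (PD 0.71, RAL 0.26 mm). Only its contrast with SRP is negative for RAL, the sign depends on the slope, and the comparison is 3 patients against 3.
- **That the six-month data are concealed or that superiority is falsely claimed.** The week-26 means are printed, and the Discussion claims significance for the regimen only on BOP.

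**Conclusion.** The point holds as a reporting gap on the primary question. Objective 1, null hypotheses 1 and 2 and the Statistical Analysis section all call for a between-arm comparison of PD and attachment over six months, and none is given in the readable text. The time-effect ANOVA and the within-arm statements cannot replace it, and the week-4 claim for HP13 attachment is contradicted by the printed means.

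The unreported differences in change are modest: +0.26 and +0.15 mm for PD, and -0.11 and +0.14 mm for RAL (HP13 and HP26 against SRP). They are exact arithmetic on the printed means. That they are inconclusive rests on the completer numbers and on the assumed patient-level SD of change of 0.3 to 0.6 mm; a much smaller true SD would narrow the intervals. On present information none of the four should be read as benefit or as absence of benefit. This should be corrected before any efficacy conclusion on PD or attachment is drawn.

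**What to change.** - Report week-26 PD and RAL per mouth by ANCOVA on baseline, each gel arm minus SRP, with patient-level 95% CIs and the 3, 3 and 9 completers stated beside them.
- State the outcome for null hypotheses 1 and 2 from those contrasts. If the intervals are uninformative, say that the hypotheses are not rejected or could not be assessed, and that this is not evidence of no effect.
- Label the repeated-measures ANOVA sentence as an overall time effect that does not bear on gel.
- Base the Abstract and Conclusion on the six-month contrasts, remove efficacy inferences drawn from within-arm change, and reconcile the week-4 claims with the printed HP13 means and with Chapter Four.

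The cost is one re-run on data already held, plus rewording. The downside is a less favourable and probably inconclusive headline.

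### Week-26 bleeding is called similar to re-evaluation in the gel arms and similar to baseline in SRP, with no interval or between-arm estimate, on 3, 3 and 9 completers

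*Combined protocol and SAP*

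**What the plan says.** Chapter Three, Results, reports mean BOP at four visits and then summarises week 26 in words. For the gel arms the summary is "with mean BOP scores at final examination staying similar to levels at re-evaluation for HP13 and HP26 groups". For the control arm it is "Mean BOP scores at final examination group for SRP group was similar to baseline". The Abstract repeats both. The gel arms are thus referred to week 13 and the SRP arm to week 0.

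The whole-mouth means behind these statements are "Baseline mean BOP was 45% for SRP, 57% for HP13, and 63.1% for HP26"; "At re-evaluation, mean BOP was 37% for SRP, 30% for HP13, and 27% for HP26"; and "Final mean BOP scores were 44% for SRP, 33% for HP13, and 28% for HP13". The last label in the final list is read here as HP26.

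The Statistical Analysis section names BOP among the primary outcomes and again among the secondary ones, and plans repeated-measures ANOVA on a per-mouth score. Its decision rule is "All comparisons were performed using two-sided hypothesis tests, and employed a 0.05 level of significance". It has no equivalence test or margin. The null hypothesis for BOP in Chapter One is a between-group one. Pocket depth, recession and attachment level are reported with standard errors; the BOP means in the text are not. Completers number 3, 3 and 9, against 20 planned per arm.

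**The concern.** A statement that two visits are similar can be supported only by an estimate of change precise enough to rule out a change that matters. Agreement of two means, or a non-significant test, does not do that in three patients.

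Two conclusions are at stake. The first is the primary objective, gel plus SRP against SRP alone over six months. BOP is the outcome on which the Discussion claims a significant effect, and the adjacent sentences suggest that the advantage lasted in the gel arms and disappeared under SRP. The second is the secondary objective, three against six months of gel. HP13 stopped gel at week 13, so calling its week-26 BOP similar to week 13 suggests that nothing was lost by stopping. Both are questions about differences between arms in change over the same interval, and the text reports no such difference.

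**Working it through.** The documents state no BOP standard deviation, interval, p-value or margin in the text, so there is no design figure to reproduce. The check uses the printed means and completer counts, with an assumed SD of per-patient change of 5, 10 or 15 points, taken as equal across arms.

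**1. Common reference visits (percentage points)**

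| Arm | Week 13 to 26 | Baseline to 26 | Share of week-13 fall later lost |
|---|---|---|---|
| SRP | 44 - 37 = +7 | 44 - 45 = -1 | 7/8 = 88% |
| HP13 | 33 - 30 = +3 | 33 - 57 = -24 | 3/27 = 11% |
| HP26 | 28 - 27 = +1 | 28 - 63.1 = -35.1 | 1/36.1 = 3% |

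The whole-mouth direction is the same on either reference. The mixed visits do not create the pattern.

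**2. Precision of change within an arm**

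The 95% half-width is t × SD/√n.
- n = 3, arm's own error (2 df): 4.303/√3 = 2.48 × SD, giving 12.4, 24.8 and 37.3 points.
- n = 3, error pooled over three arms (15 - 3 = 12 df): 2.179/√3 = 1.26 × SD, giving 6.3, 12.6 and 18.9.
- n = 9, own error (8 df): 2.306/3 = 0.769 × SD, giving 3.8, 7.7 and 11.5.

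At SD 10:

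| Change | Own error | Pooled error |
|---|---|---|
| HP13, week 13 to 26 (+3) | -21.8 to +27.8 | -9.6 to +15.6 |
| SRP, baseline to 26 (-1) | -25.8 to +23.8 | -13.6 to +11.6 |
| HP26, week 13 to 26 (+1) | -6.7 to +8.7 | -6.3 to +8.3 |

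(HP26 pooled: 2.179/3 × 10 = 7.3.)

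For scale only, take a margin of ±10 points, which is not in the documents. A 90% interval from the arm's own error fits inside it if the SD is below (10 - 3)/(2.920/√3) = 4.2 in HP13, (10 - 1)/(2.920/√3) = 5.3 in SRP against baseline, and (10 - 1)/(1.860/3) = 14.5 in HP26. With pooled error (t = 1.782) the limits are 6.8, 8.7 and 15.1.

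**3. Between-arm difference in change, week 13 to 26**

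The half-width is t × SD × √(1/n1 + 1/n2).
- HP13 minus SRP: 3 - 7 = -4. With 4 df the factor is 2.776 × √(2/3) = 2.267; pooled, 2.179 × √(2/3) = 1.779. Zero is excluded only if the SD is below 4/2.267 = 1.8, or 4/1.779 = 2.2. With 4 df the interval is -15.3 to +7.3 at SD 5 and -26.7 to +18.7 at SD 10.
- HP26 minus SRP: 1 - 7 = -6. With 10 df the factor is 2.228 × √(1/9 + 1/3) = 1.485; pooled, 1.453. Zero is excluded only if the SD is below 4.0, or 4.1. With 10 df the interval is -13.4 to +1.4 at SD 5 and -20.9 to +8.9 at SD 10.
- HP26 minus HP13: 1 - 3 = -2, with the same factors. Zero is excluded only if the SD is below about 1.3 to 1.4.

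**4. Depth strata, week 13 to 26**

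In pockets initially under 5 mm the changes are +6 (SRP, 27 to 33), +5 (HP13, 21 to 26) and 0 (HP26, 22 to 22). In deeper pockets the text gives "Re-evaluation BOP % was 91% for SRP, 78% for HP13, and 75% for HP26" and "At final examination, BOP % was 88% for SRP, 79% for HP13, and 78% for HP26", so the changes are -3, +1 and +3 and the order reverses. These figures need reconciling before anything rests on them. The deep-pocket share implied by (overall - shallow)/(deep - shallow) moves in SRP from (45 - 24)/(92 - 24) = 0.31 at baseline to (44 - 33)/(88 - 33) = 0.20 at week 26. In HP26 it moves from (63.1 - 52)/(91 - 52) = 0.28 to (28 - 22)/(78 - 22) = 0.11. Strata fixed by initial depth should keep a roughly constant share.

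**The case against.** The strongest reply is that the wording is descriptive. It tracks the printed means (44 against 45, 33 against 30, 28 against 27), and the text says so explicitly elsewhere when it means a test. A reader might infer a formal equivalence claim, or a stated conclusion that gel holds the benefit while SRP loses it. The documents support neither reading: no sentence says this, the Discussion claims only a significant reduction in BOP, the Conclusion does not mention BOP, and nothing explicit is said about the cost of stopping gel. That part of the reply stands.

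A reader might also infer that the changing reference visit manufactures the contrast. It does not: on one reference the whole-mouth direction is unchanged, and SRP gave back 7 of its 8 points. The mixed visits are a reporting flaw.

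Third, precision depends on the model. The plan is repeated-measures ANOVA. If it pools error across arms, the 3-patient half-width is about half the single-arm figure, and at SD 10 the SRP interval from baseline no longer includes the 24-point fall seen in HP13; that would need an SD above (24 - 1)/1.258 = 18.3. This stands, and both versions are shown for that reason. It does not rescue the comparison of arms, where the SD limits barely move.

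Finally, the mean-BOP figure is not shown and may carry error bars, so the absence of an interval is established for the text only.

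**Conclusion.** The point holds as a reporting and inference fault of moderate weight; the statements should be changed. Similarity is not shown in either 3-patient arm unless the SD of change is very small. To say that the data cannot support it in HP26 would go too far: with nine patients and a 1-point change the claim might be defensible, but it cannot be judged from what is reported. The main gap is the between-arm difference in change with its uncertainty. At the observed means that difference separates from zero only with an SD of about 2 points (HP13 minus SRP) or 4 points (HP26 minus SRP).

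This rests on the assumed SDs and their equality across arms, on reading the last final value as HP26, and on 3, 3 and 9 as the numbers behind the means. The last is not fully certain, because the sex counts in Results add to 18 (10 + 8) against 15 completers. The statement about weeks 4 to 13 in the same paragraph is not at issue here.

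**What to change.** In the Abstract and in Chapter Three, replace the three similarity statements with each arm's per-patient BOP change from week 13 to 26 and from baseline to 26, with 95% CIs. Add HP13 minus SRP, HP26 minus SRP and HP26 minus HP13 in those changes, with 95% CIs, as group-by-visit contrasts from the repeated-measures model already planned. Do not pool HP13 with HP26 after week 13, because one arm is then off gel and the other on it. Where an interval is wide, say that maintenance or relapse of bleeding is inconclusive.

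In Statistical Analysis, add that a non-significant change is not to be reported as similar or maintained. If the investigators want such a claim, they must name a margin. A margin chosen now, with the week-26 means known, must be labelled post hoc and gives no confirmatory protection.

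Correct or confirm the label on the last final BOP value. The per-patient BOP values are already collected, so the cost is a short reanalysis and a less favourable week-26 statement.
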